6.5. Criteria for Study Termination

If more than 2 of the first 6 patients enrolled in the first stage of the study experience treatment-limiting toxicity within the first 4 weeks of their treatment, the protocol will be modified or the study will be stopped. If after the first 25 patients have been enrolled in the study, 2 or fewer patients have had a confirmed ccRCC tumor response of PR or better, further enrollment will be temporarily suspended for up to a year or until at least 3 confirmed responses are seen. If 3 confirmed responses have not been observed within1 year after enrollment of the 25th patient, no further patients will be enrolled and the study will be stopped.

A Data Monitoring Committee (DMC) will perform the safety review for the first 6 patients and the futility analysis for Stage 1 of the study. The DMC will consist of the Principal Investigator(s) participating in this study, the Medical Monitor, and representatives from Peloton. The DMC will meet shortly after the sixth patient has been observed for 28 days after the administration of their initial PT2385 dose. The DMC will review safety and any treatment-limiting toxicities to confirm whether the study should continue to enroll or if modifications to the protocol are needed. The DMC will review the response data from the first 25 patients to determine if at least 3 patients have a confirmed PR or better in ccRCC tumors and that the threshold for opening Stage 2 has been met. Treatment-limiting toxicities will be assessed according to Section 6.4.

7. SELECTION AND WITHDRAWAL OF PATIENTS

7.1. Informed Consent

Written informed consent (see Section 16.3) must be obtained from the patient before any study related procedures are performed and whenever the study procedures change or new safety information becomes available that may affect the patient's willingness to participate.

Male patients must be provided with information about the option for sperm banking before providing written informed consent.

7.2. Patient Eligibility

Inclusion and exclusion criteria should be reviewed during the time period indicated for Screening in Appendix 1, Schedule of Events. Patients must meet all of the inclusion and none of the exclusion criteria for study entry.

7.2.1. Patient Inclusion Criteria

Patients must meet all of the following criteria to be enrolled in this study.

- 1. Has the ability to understand and willingness to sign a written informed consent form before the performance of any study procedures
- 2. Is of age ≥ 18 years
- 3. Has at least 1 measurable ccRCC tumor and no solid ccRCC tumor > 3.0 cm, based on radiologic diagnosis (histologic diagnosis not required); may have VHL disease-associated lesions in other organ systems
- 4. Has a diagnosis of von Hippel-Lindau disease, based on a germline VHL alteration
- 5. Has an Eastern Cooperative Oncology Group (ECOG) performance status of 0 to 2 (see Appendix 2)
- 6. Has normal organ and marrow function as defined below:
 - White blood cell count $\geq 3,000/\mu L$, absolute neutrophil count $\geq 1,500/\mu L$, hemoglobin level ≥ 9 g/dL without transfusion support within 2 weeks prior to enrollment; platelet count $\geq 100,000/\mu L$;
 - Serum creatinine level $\leq 2.0 \times$ ULN or measured 24-hour creatinine clearance ≥ 30 mL/min; and
 - Levels of AST and ALT < $2.5 \times$ ULN, total bilirubin < $1.5 \times$ ULN (< $3 \times$ ULN in patients with Gilbert's disease), and alkaline phosphatase $\leq 2.5 \times$ ULN

- 7. If a female patient of child-bearing potential, or a male patient with a female partner of child-bearing potential (defined as all women physiologically capable of becoming pregnant), must agree to use highly effective methods of contraception during screening, during the period of drug administration and for 30 days after stopping study drug administration. Highly effective contraception methods include the following:
 - Total abstinence,
 - Male or female sterilization, or
 - Combination of any 2 of the following (a + b or a + c or b + c):
 - a. Use of oral, injected or implanted hormonal methods of contraception
 - b. Placement of an intrauterine device (IUD) or intrauterine system (IUS)
 - c. Barrier methods of contraception: condom or occlusive cap (diaphragm or cervical/vault caps) with spermicidal foam/gel/film/cream/vaginal suppository
- 8. If a female patient of child-bearing potential, must have a negative serum pregnancy test result within 7 days before first administration of study drug.

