PT2385 induced concentration-dependent increases in CYP2B6 and CYP3A4 mRNA in cultured human hepatocytes. Simcyp physiologically-based pharmacokinetic (PBPK) model simulations indicate a weak-to-moderate CYP3A4 substrate midazolam drug-drug interaction (DDI) (~50% reduction in midazolam AUC) at the clinical relevant PT2385 doses. A qualitative assessment of the DDI liability of sunitinib, cabozantinib, and axitinib when co-administered with PT2385 was performed using literature data; the expected DDI effects with these kinase inhibitors are smaller than the effect predicted for midazolam. Simulations also indicate that PT2385 is a weak CYP2B6 inducer (< 11% AUC reduction for CYP2B6 substrate bupropion at the clinical relevant PT2385 doses).

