8.2. Concomitant Medications

Patients may not receive chemotherapy, anti-neoplastic hormonal therapy, or any investigational anti-neoplastic agent during the course of this study. Immunosuppressive agents are prohibited during the course of study participation. Systemic steroids may not be used in the study at doses greater than the equivalent of 20 mg prednisone daily with the exception of intermittent use for the treatment of emesis.

Patients may receive limited fraction palliative radiotherapy after 12 weeks to control local tumor-related symptoms if irradiation is unlikely to induce major organ toxicity and only if in the opinion of the Investigator, the patient does not have progressive disease. The radiation field cannot encompass a target lesion. Radiation to a target lesion is considered progressive disease and the patient should be removed from study treatment.

Antiemetic agents may be used for the treatment of nausea and vomiting but may not be administered prophylactically. Granulocyte colony-stimulating factor (G-CSF) should be administered only for severe or prolonged neutropenia or for neutropenic sepsis. There will be no constraint on the use of growth factors during subsequent treatment; however, prophylactic use is discouraged and adherence to the American Society of Clinical Oncology (ASCO) guidelines is recommended. Erythropoietin should not be administered during the first 28 days of study drug treatment.

Patients should receive all necessary supportive care, including blood products, transfusions, antibiotics, pain medications, bisphosphonates, and replacement hormonal therapies (insulin, thyroid hormones, estrogen/progesterone) as needed, but levels should be closely monitored.

PT2385 is primarily metabolized by UGT2B17, UGT2B7, UGT2B15, CYP2C19 and CYP3A4. Strong inhibitors of CYP2C19 and CYP3A4 should be avoided in patients receiving PT2385 (Appendix 6).

PT2385 has been shown to induce the enzymes CYP3A4 and CYP2B6 in cultured human hepatocytes. Simcyp PBPK model simulations indicate weak-to-moderate CYP3A4 substrate midazolam DDIs (~50% reduction in midazolam AUC) at the clinically relevant PT2385 doses. Simulations also indicate that PT2385 is a weak CYP2B6 inducer (< 11%

Peloton Therapeutics, Inc. CONFIDENTIAL

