AUC reduction for CYP2B6 substrate bupropion at the clinically relevant PT2385 doses). PT2385 is not a potent inhibitor for CYP1A2, CYP2B6, CYP2C8, CYP2C9, CYP2C19, CYP2D6 and CYP3A4 (IC₅₀ > 8.8 μ g/mL). It is unlikely to significantly inhibit these CYPs at the clinically relevant PT2385 concentrations (C_{max} ~ 3.14 μ g/mL). A partial list of CYP3A4, CYP2B6, CYP2C9, and CYP2C19 substrates is provided in Appendix 7.

Patients taking medications metabolized by CYP3A4 and CYP2B6 should be monitored carefully for decreases in drug effect. Patients taking medications metabolized by CYP2C9 and CYP2C19 should be monitored for potential increases in drug effect.

All concomitant medication(s) used during the study and within 28 days before the start of study drug administration will be reported on the appropriate CRF page.

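### The contraception rule rates hormonal plus barrier as highly effective for women taking PT2385, without a warning that the drug's predicted CYP3A4 induction may weaken the hormonal part

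*Combined protocol and SAP*

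**What the plan says.** Criterion 7 in the Synopsis and in 7.2.1 opens its list with "Highly effective contraception methods include the following". It then accepts abstinence, sterilization, or two methods out of three: "Combination of any 2 of the following (a + b or a + c or b + c"). The first of the three is "a. Use of oral, injected or implanted hormonal methods of contraception", the second an IUD or IUS, and the third a condom or cap with spermicide. Section 12.8.1 gives the same list without the highly effective label. In all three places one list serves both female patients and the female partners of male patients, from screening until 30 days after the last dose.

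On the interaction, 8.2 states: "PT2385 has been shown to induce the enzymes CYP3A4 and CYP2B6 in cultured human hepatocytes". Section 4.1.2.2 gives the simulated size, as an approximate figure: "50% reduction in midazolam AUC) at the clinical relevant PT2385 doses". Sections 4.1.2.2 and 8.2 both call the interaction weak to moderate. The substrate table in Appendix 7 puts estradiol in the CYP3A4 column and progesterone in the CYP2C19 column.

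The management instruction in 8.2 is general: "Patients taking medications metabolized by CYP3A4 and CYP2B6 should be monitored carefully for decreases in drug effect". For CYP2C9 and CYP2C19 drugs it asks for the opposite, a watch for increased effect. Hormones appear in 8.2 only as supportive care: "replacement hormonal therapies (insulin, thyroid hormones, estrogen/progesterone) as needed, but levels should be closely monitored". That concerns replacement, not contraception.

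**The concern.** Two parts of the protocol have not been brought together. The pharmacology sections treat PT2385 as a likely CYP3A4 inducer and tell investigators to expect some loss of effect from CYP3A4 drugs. The contraception rule takes no account of this and treats a woman exposed to the inducer like a partner who is not exposed.

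Unless a patient is abstinent or covered by sterilization, the protocol wants two methods. If hormone exposure falls, a + c leans more heavily on the barrier than the rule assumes, and no text names this risk to the investigator. Monitoring for reduced effect helps when loss of effect can be seen and reversed. With a contraceptive, the visible loss of effect is a pregnancy. A pregnancy test, or stopping the drug once pregnancy is confirmed (12.8.2), comes after exposure of the fetus.

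The fetal hazard is unknown from these documents. Section 4.1.2.3 reports no target organ in female rats or dogs and negative genotoxicity assays, and describes no embryo-fetal study. The Investigator's Brochure, which may add to this, is not available here.

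**Working it through.** No design figure bears on this point. The one related number, the midazolam result, comes from a simulation whose inputs are not in the protocol, so it cannot be reproduced. Three checks are possible.

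**1. Which pairs are exposed.** The permitted pairs are a + b, a + c and b + c. Two contain an IUD/IUS; one, a + c, does not. So 1 of 3 pairs relies on a systemic hormone with only a barrier behind it.

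**2. How far hormone exposure might fall (illustration only).** Take AUC ratio = 1 / (1 + fm × (E − 1)). Here fm is the share of a drug's clearance through CYP3A4, and E is the fold-increase in that pathway. Set E so that midazolam gives 0.5: E = 1 + (1/0.5 − 1) / fm(midazolam). The documents give no fm for any drug, so every fm below is an assumption.

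| fm of the steroid | AUC left if fm(midazolam) = 1.0, E = 2.00 | AUC left if fm(midazolam) = 0.9, E = 2.11 |
|---|---|---|
| 0 | 100% | 100% |
| 0.25 | 80% | 78% |
| 0.50 | 67% | 64% |
| 0.75 | 57% | 55% |
| 1.00 | 50% | 47% |

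The direction is a fall whenever fm is above zero. The size runs from no change to roughly half, depending on values the protocol does not give. The model also treats oral, injected and implanted methods alike.

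**3. Longest gap between scheduled pregnancy tests.** Inputs are the visit windows in Appendix 1 footnote 1, the test schedule in footnote 9, and the Extended Treatment column with footnote 2. Gap = planned days + window at the first visit + window at the second.

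- Weeks 1 to 3: 14 + 0 + 1 = 15 days
- Weeks 3 to 5: 14 + 1 + 1 = 16 days
- Weeks 5 to 9: 28 + 1 + 2 = 31 days
- Later 4-weekly visits: 28 + 2 + 2 = 32 days
- After 1 year, if tests follow the 12-week visits: 84 + 7 + 7 = 98 days

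The last line conflicts with footnote 9, which keeps tests every 4 weeks. Yet the pregnancy-test row is marked under Extended Treatment, and footnote 2 moves visits to 12-week intervals. The protocol does not say which applies.

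**The case against.** The strongest objection is that the decisive link is missing. The evidence is induction in hepatocytes plus a simulation with a different drug. No contraceptive steroid was studied, and Appendix 7 names estradiol without tying it to any contraceptive product. For the three kinase inhibitors considered in 4.1.2.2, "the expected DDI effects with these kinase inhibitors are smaller than the effect predicted for midazolam". Progesterone, the only progestogen listed, is in the CYP2C19 column, where 8.2 warns of increased effect. All of this stands. It limits the claim to a possible, partial weakening of unknown size.

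A second objection is that the protocol already has safeguards. No hormonal method is accepted alone; 8.2 describes the induction and points to the table that lists estradiol; a serum test precedes dosing, urine tests follow, and drug is held on suspicion of pregnancy. These are real protections, and the barrier in a + c is one of them. But apart from the barrier they either detect failure or leave the investigator to make the connection. None changes how a + c is described to a treated woman.

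A reader might infer that a + c should be barred for female patients. The documents do not support that. Both remaining pairs contain an IUD/IUS, so a ban would make the device compulsory for every fertile woman who is neither abstinent nor covered by sterilization. In a rare disease at up to 3 centers, that is a procedural entry condition resting on simulated data for another drug.

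Finally, the consent form and the Investigator's Brochure are not available here and may already carry such advice. If so, the protocol should still agree with them.

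**Conclusion.** The point holds as a gap in participant-safety wording. The protocol rates a + c highly effective for women taking PT2385 while predicting an interaction that may reduce the hormonal component, and it does not connect the two. One of three permitted pairs is affected. Under the assumed CYP3A4 shares, remaining hormone exposure would be between about 47% and 100% of usual. The documents do not show where in that range any contraceptive lies, or whether such a fall would matter clinically.

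It would be wrong to conclude that hormonal contraception fails on PT2385 or that a fetal hazard has been shown; neither is in the documents. The number of women who would use a + c is not given and is not estimated here. The concern does not extend to untreated partners of male patients. A warning and a counselling rule are justified because they cost almost nothing; a restriction on eligibility is not.

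**What to change.** In 8.2, directly after the CYP3A4/CYP2B6 monitoring sentence, add: *Hormonal contraceptives may be less effective during PT2385 treatment because PT2385 may induce CYP3A4; see 12.8.1.*

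In the Synopsis (criterion 7), 7.2.1 (criterion 7) and 12.8.1, add for female patients only: *From the first dose until 30 days after the last dose, a hormonal method should not be relied on as the main method; a pair that includes an IUD/IUS is preferred, and a woman who uses a + c must be told of the possible interaction and use the barrier with spermicide consistently.*

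Put matching wording in the consent form. Leave the options for untreated partners as they are. Do not make an IUD/IUS mandatory unless interaction data with a contraceptive steroid support it. The conflict between footnote 9 and the Extended Treatment column should also be settled, but this change does not depend on it.

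The cost is one sentence in 8.2, one in each of three other places, the consent edit, and slightly longer counselling. A few women may choose to switch method; the screening window of up to 28 days leaves time for that. No woman becomes ineligible.

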7.2.2. Patient Exclusion Criteria

Patients will be excluded from this study if they meet any of the following criteria.

- 1. Has participated or plans to participate in another clinical trial of an investigational drug (or a medical device) within 30 days of study enrollment
- 2. Has had prior treatment with or known allergy or sensitivity to a HIF α inhibitor
- 3. Has had prior radiotherapy or systemic anti-cancer therapy for ccRCC (includes anti-VEGF therapy or any systemic investigational anti-cancer agent)
- 4. Has a prior or concomitant non-VHL disease-associated invasive malignancy with the exception of adequately treated basal or squamous cell carcinoma of the skin, cervical carcinoma in situ or any other malignancy from which the patient has remained disease free for more than 2 years
- 5. Has any history of metastatic disease
- 6. Has any condition possibly affecting absorption, distribution, metabolism or excretion of drugs that may confound the analyses conducted in this study (e.g., previous surgery on the gastrointestinal tract that includes removal of parts of stomach, bowel, liver, gallbladder, or pancreas)
- 7. Has known hypersensitivity to any component in the formulation of PT2385
- Has had radiotherapy to any non-ccRCC site within 4 weeks prior to entering the study or has not recovered from adverse events (AE) (to ≤ Grade 1 NCI CTCAE 4.03) related to agents administered more than 4 weeks earlier

- 9. Has had any surgical procedure for VHL disease or any major surgical procedure completed within 4 weeks prior to entering the study or has any surgical lesions from recent major surgical procedures that are not well healed
- 10. Has an immediate need for surgical intervention for tumor treatment.
- 11. Has known history of positive test results for human immunodeficiency virus (HIV) or known acquired immunodeficiency syndrome (AIDS)
- 12. Has an active infection requiring systemic treatment
- 13. Has a bleeding diathesis or coagulopathy
- 14. Has had any major cardiovascular event within 6 months prior to study drug administration including but not limited to myocardial infarction, unstable angina, cerebrovascular accident, transient ischemic event, pulmonary embolism, or New York Heart Association Class III or IV heart failure (see Appendix 5)
- 15. Has any other clinically significant cardiac, respiratory, or other medical or psychiatric condition that might interfere with participation in the trial or interfere with the interpretation of trial results
- 16. If a female patient, intends to breast feed a child during study or within 30 days after administration of the last dose of study drug.

7.2.3. Patient Withdrawal Criteria

Patients have the right to withdraw from the study or study treatment at any time for any reason. The Investigator may discontinue a patient from the study or study treatment for any of the following reasons:

- Disease progression per RECIST 1.1
- Occurrence of an AE, development of an intercurrent illness/condition, or change in patient's condition that leads the Investigator to be concerned about the patient's welfare
- Treatment-limiting toxicity or intolerable toxicity
- Noncompliance with study procedures
- Failure to comply with study drug administration instructions, to return for follow up, or to meet other requirements of the study
- Pregnancy in a female patient during the study
- Death
- Withdrawal of consent

The reason for a patient's withdrawal from the study or study treatment will be recorded in the case report form (CRF). Patients who withdraw from study participation for any reason may not re-enter the study at any time.

Patients who discontinue from study treatment will be asked to complete the early termination and safety follow-up procedures according to the Schedule of Events, Appendix 1. During the safety follow-up the patient should be evaluated for continuation or resolution of any treatment-related AEs/SAEs

Long-term follow-up will begin at the time a patient discontinues study treatment for any reason and will continue for up to 3 years following completion of enrollment in the study or until the patient withdraws consent or dies.

8. TREATMENT OF PATIENTS

8.1. Description of Study Drug

Table 2Investigational Product

	Investigational Product	
Product Name	PT2385	
Dosage Form	Tablet	
Unit Dose	200 mg	
Route of Administration	Oral	
Physical Description	White capsule-shaped tablet	
Manufacturer	Peloton Therapeutics, Inc., Dallas, TX	

8.2. Concomitant Medications

Patients may not receive chemotherapy, anti-neoplastic hormonal therapy, or any investigational anti-neoplastic agent during the course of this study. Immunosuppressive agents are prohibited during the course of study participation. Systemic steroids may not be used in the study at doses greater than the equivalent of 20 mg prednisone daily with the exception of intermittent use for the treatment of emesis.

Patients may receive limited fraction palliative radiotherapy after 12 weeks to control local tumor-related symptoms if irradiation is unlikely to induce major organ toxicity and only if in the opinion of the Investigator, the patient does not have progressive disease. The radiation field cannot encompass a target lesion. Radiation to a target lesion is considered progressive disease and the patient should be removed from study treatment.

Antiemetic agents may be used for the treatment of nausea and vomiting but may not be administered prophylactically. Granulocyte colony-stimulating factor (G-CSF) should be administered only for severe or prolonged neutropenia or for neutropenic sepsis. There will be no constraint on the use of growth factors during subsequent treatment; however, prophylactic use is discouraged and adherence to the American Society of Clinical Oncology (ASCO) guidelines is recommended. Erythropoietin should not be administered during the first 28 days of study drug treatment.

Patients should receive all necessary supportive care, including blood products, transfusions, antibiotics, pain medications, bisphosphonates, and replacement hormonal therapies (insulin, thyroid hormones, estrogen/progesterone) as needed, but levels should be closely monitored.

PT2385 is primarily metabolized by UGT2B17, UGT2B7, UGT2B15, CYP2C19 and CYP3A4. Strong inhibitors of CYP2C19 and CYP3A4 should be avoided in patients receiving PT2385 (Appendix 6).

PT2385 has been shown to induce the enzymes CYP3A4 and CYP2B6 in cultured human hepatocytes. Simcyp PBPK model simulations indicate weak-to-moderate CYP3A4 substrate midazolam DDIs (~50% reduction in midazolam AUC) at the clinically relevant PT2385 doses. Simulations also indicate that PT2385 is a weak CYP2B6 inducer (< 11%

Peloton Therapeutics, Inc. CONFIDENTIAL
AUC reduction for CYP2B6 substrate bupropion at the clinically relevant PT2385 doses). PT2385 is not a potent inhibitor for CYP1A2, CYP2B6, CYP2C8, CYP2C9, CYP2C19, CYP2D6 and CYP3A4 (IC₅₀ > 8.8 μ g/mL). It is unlikely to significantly inhibit these CYPs at the clinically relevant PT2385 concentrations (C_{max} ~ 3.14 μ g/mL). A partial list of CYP3A4, CYP2B6, CYP2C9, and CYP2C19 substrates is provided in Appendix 7.

Patients taking medications metabolized by CYP3A4 and CYP2B6 should be monitored carefully for decreases in drug effect. Patients taking medications metabolized by CYP2C9 and CYP2C19 should be monitored for potential increases in drug effect.

All concomitant medication(s) used during the study and within 28 days before the start of study drug administration will be reported on the appropriate CRF page.

